## 7 SAMPLE SIZE AND POWER

According to the protocol, a sample size of  $n = 15$  subjects per group will provide at least 80% power to detect a difference of at least 50% in A4 mean percent change from baseline between a given dose level of tildacerfont and placebo, assuming a common SD of 30%.

An assumed dropout rate of 15% during the Treatment Period results in a target of 18 subjects per group and a total sample size of 72 subjects who enter the Treatment Period.

## **8 ANALYSIS SETS**

### **8.1 Intent-To-Treat Analysis Set**

The Intent-To-Treat (ITT) Analysis Set will include all randomized subjects regardless of Treatment Period eligibility or completion. The ITT Analysis Set will be the basis for demographics, baseline characteristics, and efficacy analyses.

### **8.2 Modified Intent-To-Treat Analysis Set**

The following modified ITT (mITT) Analysis Sets will include all randomized subjects who receive at least 1 dose of study drug (tildacerfont or placebo), have at least 1 post-baseline A4 assessment, and did not change background GC through Week 18.

### **8.3 Per-Protocol Analysis Set**

The Per-Protocol (PP) Analysis Set for Part A of the Treatment Period will include all eligible subjects who have no major protocol deviations that would affect the analysis of efficacy data. The PP Analysis Set may be used for supportive secondary analyses of the primary and secondary efficacy endpoints.

Major protocol deviations that would affect the analysis of efficacy data are listed as the following, but not limited to:

- Randomization error
- Subject did not meet efficacy-based inclusion criteria (elevated biomarkers)
- Subject met efficacy-based exclusion criteria (use of dexamethasone, night-shift worker), without waiver
- Subject's aggregate drug compliance was < 80% over the Treatment Period

Additional deviations will be identified prior to database lock and updated in this section.

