Immediately following the Weeks 18 and 24 visits, subjects will continue to take their previously assigned study drug until A4 laboratory results are received, the randomization and trial supply management (RTSM) system determines the appropriate tildacerfont doses for the next portion of the study, and subjects receive their tildacerfont doses for the next portion of the study.

During the optional Open-Label Extension Period, subjects will continue to receive tildacerfont at 200 mg QD.

On the evenings before scheduled laboratory assessments, subjects should take their evening GC dose before 10 PM. On the mornings of scheduled laboratory assessments, subjects should delay taking any

morning dose of GC medication until after the 8 AM (± 1 hour) laboratory assessments have been completed. On all other days during the study, subjects should take their GC medication at the usual time(s). Mineralocorticoid may be taken at any time of day, but its timing relative to laboratory assessments should be consistent throughout the study.

During times of clinically significant physical stress such as intercurrent illness with fever, surgical procedures, or significant trauma, stress dosing with extra GC (in the form of HC) for prevention of adrenal crisis will be allowed according to “sick day guidelines” (see [Section 6.5.1.5](#)). The Sponsor will provide GC for periods of stress dosing.

Study drug will be discontinued in subjects who meet individual treatment-stopping criteria (see [Section 7.1](#)).

Study Duration

The expected duration of study participation for each subject is up to approximately 86 weeks. This includes a Screening Period of ≤ 45 days, a placebo Run-in Period of 6 weeks, a Treatment Period of 70 weeks, and a safety follow-up period of approximately 30 days. Subjects who continue in the optional Open-Label Extension Period will participate for up to an additional 240 weeks.

Statistical Analyses

Statistical Hypotheses

For the Primary Efficacy Analysis, the null hypothesis is that there is no difference in the profile of log A4 change from baseline through 12 weeks of blinded randomized treatment between tildacerfont and placebo. The alternative hypothesis is that there is difference in the profile of log A4 change from baseline through 12 weeks of blinded randomized treatment between tildacerfont and placebo.

Sample Size

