9.3 Populations for Analyses

The ITT Population will include all randomized subjects regardless of Treatment Period eligibility or completion. The ITT Population will be the primary analysis set for analyzing demographics, baseline characteristics, and efficacy analyses.

The mITT Population is all randomized subjects who receive at least 1 dose of study drug (tildacerfont or placebo), have at least 1 post-baseline A4 assessment, and did not change background GC through Week 18

The PP Population for each part of the Treatment Period will include all eligible subjects who have no major protocol deviations that would affect the analysis of efficacy data (defined below). The PP Population may be used for secondary analyses of the primary and secondary efficacy endpoints. Additional criteria for the PP Population may be specified in the SAP. The PP Population will be identified prior to database lock.

Major protocol deviations that would affect the analysis of efficacy data are defined as the following:

- Subject did not meet efficacy-based inclusion criteria (elevated biomarkers)
- Subject met efficacy-based exclusion criteria (use of dexamethasone, night-shift worker)
- Subject's drug compliance was <80% over the Treatment Period

Additional criteria may be specified in the SAP.

The Safety Population will include all subjects who receive at least 1 dose of study drug (tildacerfont or placebo) during the Treatment Period, summarized by actual drug received. The Safety Population will be the primary analysis set for general and safety analyses.

The PK Population will include all randomized subjects who receive at least 1 dose of tildacerfont and have at least 1 evaluable PK sample.

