## 5 STUDY DESIGN

This is a multi-center, randomized, double-blind, placebo-controlled, dose-ranging clinical study with a 3-part Treatment Period and an optional Open-Label Extension Period. The 3-part Treatment Period will evaluate the efficacy and safety of up to 70 weeks of treatment with tildacerfont in adult subjects with classic CAH who have elevated biomarkers at baseline. At least 72 adult subjects will be randomized into the Treatment Period of the study.

A 6-week, single-blind, placebo Run-in Period, will assess subjects for adherence to their existing GC therapy and daily ingestion of placebo with food. Upon completion of a 6-week single-blind, placebo Run-in Period, subjects who meet all eligibility criteria will be randomized into the Treatment Period. Subjects will be randomized in a 1:1:1:1 ratio to receive either tildacerfont at a dose of 50 mg (once daily) QD, 100 mg QD, and 200 mg QD or matching placebo along the randomization stratum (Week 4 A4  $\leq$  4  $\times$  upper limit of normal [ULN] versus Week 4 A4  $>$  4  $\times$  ULN). The first 12 weeks of the treatment period constitute the randomized, double blind, placebo-controlled, dose finding treatment period (Part A).

Following Part A, all subjects will receive tildacerfont for duration of 12 weeks (Part B) with opportunities to up-titrate their tildacerfont dose up to 200 mg QD based on treatment response. Placebo subjects will receive the 100 mg tildacerfont QD dose at the beginning of Part B. Part B will have possible dose escalations at Week 18 and Week 24 for eligible subjects not meeting androstenedione (A4) response criteria as an assessment of dose titration for non-responders (A4  $>$  upper limit of normal [ULN]).

Part C is a 46-week treatment period in which all subjects are escalated to receive 200 mg tildacerfont QD at Week 30, with opportunities for glucocorticoid (GC) reduction for eligible subjects (subjects meeting A4  $\leq$  ULN).

Subjects continuing into the optional Open-Label Extension Period will receive 200 mg tildacerfont QD for up to 240 weeks of treatment, with opportunities for GC adjustment for eligible subjects at each visit. Upon completion of the Open-Label Extension Period or completion of Treatment Period Part C for those subjects who do not continue into the Open-Label Extension Period, subjects will return to the clinic within 30 days following their last dose for a Follow-up visit.

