Clinical visits during Parts A, B, and C in the Treatment Period, the Open-Label Extension Period, and Follow-up Period will include efficacy, biomarkers, safety, and pharmacokinetic (PK) assessments. [Figure 1](#) depicts study visits from Screening Period to Follow-up Period and [Figure 2](#) depicts study visits during the optional Open-Label Extension Period.

The maximum duration per subject of the main Treatment Period of Study SPR001-203 is expected to be up to 87 weeks (i.e., a maximum of 45-day Screening Period, a 6-week Run-in Period, a 70-week Treatment Period, and a 30-day safety Follow-up Period). Including the optional Open-Label Extension Period (240 weeks), the maximum duration per subject is expected to be up to 327 weeks. Subjects randomized to tildacerfont in Part A will receive up to 70 weeks of treatment with tildacerfont in the main study. For subjects randomized to placebo in Part A, this will include up to 58 weeks of treatment with tildacerfont in the main study. Assessments and procedures for evaluation of safety, efficacy, PK, and biomarkers will be conducted per the protocol-specified schedule (see Appendix A: [Table 13](#), [Table 14](#), and [Table 15](#)).

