### 13.3.5.2 Per-Protocol Analysis and mITT Sets

The primary analysis of A4 as described in [Section 13.3.3](#) will be repeated in the PP and mITT Analysis Sets ([Section 8.3](#)) as supportive analyses.

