## 15 CHANGES RELATIVE TO THE PROTOCOL-SPECIFIED ANALYSIS

Protocol Section 4.4.1 defines the completion of study treatment as completing “all visits through Week 76 of the Treatment Period.” In the SAP [Section 9.3.4](#), the end of study treatment is redefined to the completion of the Week 76 visit to remove the ambiguity surrounding the classification of subjects with missed or out-of-window visits.

Protocol Section 4.4.2 defines the end of the study as completing “all phases of the study, including the final follow-up visit.” In the SAP [Section 9.3.5](#), the end of study treatment is clarified as the completion of the three Treatment Period parts as well as the final Follow-up visit

Protocol Section 8.1.2.2 identifies the Patient Global Impression of Change and Protocol Section 8.1.2.2 identifies the Clinical Global Impression – Improvement Scale as efficacy assessments that evaluate the quality of life. Given that the protocol synopsis and Protocol Section 3 Objectives and Endpoints do not mention PGIC and CGI-I as efficacy assessments, these assessments will be listed as described in SAP [Section 14.6](#).

The mITT Population was defined in Protocol Section 9.3 as all randomized subjects who receive at least 1 dose of study drug (tildacerfont or placebo), have at least 1 A4 assessment, and did not change background GC through Week 18. This definition has been updated to specify

that subjects must have at least one post-baseline A4 assessment in order to make this population relevant to the efficacy analyses.

The Per-Protocol Analysis Set for each part of the Treatment Period was defined in Protocol Section 9.3 as all eligible subjects who have no major protocol deviations that would affect the analysis of efficacy data. This definition has been updated to only pertain to Part A of the Treatment Period in order to align with the analyses of the primary and secondary endpoints.

Since Protocol Section 6.1 defines study drug as either tildacerfont or placebo, the Safety Analysis Set should include all subjects treated with study drug, which includes the single-blinded placebo Run-in Period. The SAP [Section 8.4](#) therefore defines the Safety Analysis Set as subjects who receive at least one dose of study drug during the Run-in or Treatment Period, and the SAP [Section 8.5](#) defines the Randomized Safety Analysis Set to serve the intention of the protocol-defined Safety population defined in Protocol Section 9.3.

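### The Part A per-protocol set excludes on drug compliance over the 70-week Treatment Period; the SAP should state a Part A window.

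*SAP*

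**What the plan says.** SAP Section 8.3 opens: "The Per-Protocol (PP) Analysis Set for Part A of the Treatment Period will include all eligible subjects". Subjects with major deviations affecting the efficacy analysis are left out. One listed deviation is that the subject's "aggregate drug compliance was < 80% over the Treatment Period".

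That bullet comes from Protocol Section 9.3, where the PP set was to be formed for each part of the treatment phase and the wording is "drug compliance was <80% over the Treatment Period". SAP Section 15 records the narrowing of the set: "This definition has been updated to only pertain to Part A of the Treatment Period". The stated reason is alignment with the primary and secondary endpoints. Section 15 does not mention the compliance window.

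The term itself is defined. SAP Section 5 says "The 3-part Treatment Period will evaluate the efficacy and safety of up to 70 weeks of treatment with tildacerfont" and, in the duration paragraph, "a 70-week Treatment Period". The protocol synopsis agrees: "a Treatment Period of 70 weeks".

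SAP Section 13.3.5.2 says the primary A4 analysis "will be repeated in the PP and mITT Analysis Sets". SAP Sections 10.3 and 13.1 place the primary analysis after all subjects complete Week 18, on hard-locked data.

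**The concern.** A PP analysis is useful here if it shows the A4 result in subjects who took their randomised drug up to Week 18. A compliance rule spanning Parts A to C measures something else. After Week 18, SAP Section 5.2.1 moves placebo subjects to active drug, and subjects on 50 or 100 mg may be escalated according to their Week 18 A4. Most of the literal window is therefore adherence to a different treatment, observed after the endpoint and possibly influenced by it.

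There is also a timing problem. Under the literal rule, compliance is complete only at Week 76, while the PP repeat belongs to the Week 18 analysis. Whoever programs the set would have to choose the window, and Section 8.3 does not say which one to use.

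**Working it through.** **Inputs**
- Part lengths: 12, 12 and 46 weeks (SAP 5.2.1).
- Visit days: Week 6 is Day 43, Week 18 is Day 127, Week 76 is Day 533 (Protocol 1.3.3).
- Compliance: tablets taken divided by tablets expected, at 4 tablets per day (SAP 9.3.23.5).
- PP cut-off: 80% (SAP 8.3).

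**Reproducing the plan's figure.** 12 + 12 + 46 = 70 weeks. By visit days, 533 − 43 = 490 days = 70 weeks. The stated length reproduces.

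**Share of the window after the endpoint**
- Part A: 127 − 43 = 84 days; 84/490 = 17.1%.
- After Week 18: 533 − 127 = 406 days; 406/490 = 82.9%.

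**Overall compliance as a weighted average.** With compliance a in Part A and b in Parts B and C, overall compliance is (12a + 58b)/70. On assumed splits, which the documents do not give:
- a = 95%, b = 75%: (11.4 + 43.5)/70 = 78.4%, excluded.
- a = 60%, b = 90%: (7.2 + 52.2)/70 = 84.9%, kept.

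**Later compliance needed to stay in the set.** b = (0.80 × 490 − 84a)/406:

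| Part A compliance | Parts B and C needed |
|---|---|
| 100% | 308/406 = 75.9% |
| 90% | 316.4/406 = 77.9% |
| 80% | 324.8/406 = 80.0% |
| 60% | 341.6/406 = 84.1% |
| 50% | 350/406 = 86.2% |
| 0% | 392/406 = 96.6% |

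So a fully compliant Part A subject is excluded if later compliance falls below 75.9%, and a subject who took nothing in Part A is kept at 96.6% or more. This shows how the rule behaves. It does not predict how many subjects would be misclassified.

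**Denominator.** The SAP does not say how early discontinuation enters the PP calculation. If the planned 490 days are used, a subject fully compliant to Week 18 who then stops scores 84/490 = 17.1%, and stopping before Week 62 gives less than 80%, since (62 − 6)/70 = 80%. If only days on drug count, the same subject scores 100%. The question remains with a Part A window: full compliance for 42 of the 84 days is 42/84 = 50% on planned days and 100% on days on drug.

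**With the window limited to Part A.** 84 × 4 = 336 expected tablets; 0.80 × 336 = 268.8, so at least 269 tablets. As written, 490 × 4 = 1,960 expected and 0.80 × 1,960 = 1,568, not known until Week 76.

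**The case against.** The strongest reply is that a Part A window is the natural reading. SAP Section 9.3.23.5 calculates compliance by treatment period, Section 9.3.23.6 names Parts A, B and C as treatment periods, Table 7 in Section 9.3.23.3 lists Part A under that label, and Section 5.1 applies the term to Part A. Section 12.1 reports Part A compliance separately and names drug accountability as the source.

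This stands as far as it goes. A reader might infer that the PP set cannot be formed at Week 18. The documents do not support that, because the Part A figure exists and a programmer could use it. But Section 8.3 itself refers to Part A *of* the Treatment Period, so there the capitalised term means the whole, and the bullet sets no narrower window.

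A reader might also infer that the PP analysis will later select on behaviour after the endpoint. That does not follow either: no PP analysis is scheduled after Week 18. SAP Section 13.2 assigns exploratory and safety analyses to Week 76.

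Nor do the documents support the inference that membership is free to change after unblinding. Protocol Section 9.3 requires the PP set to be identified before database lock, and SAP Sections 8.3 and 11.2 require deviations to be settled by then. What they leave open is which lock is meant, since Section 10.3 has a Week 18 hard lock and Section 13.2 a later data freeze.

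Finally, the PP analysis is supportive. The primary analysis is on the ITT set under a treatment-policy approach that includes non-compliant subjects (SAP 13.3.1).

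**Conclusion.** The wording defect holds. The set was narrowed to Part A and its compliance window was not, so the literal criterion draws 82.9% of its days from after the endpoint. This rests on the documents' own definition of the Treatment Period and on planned visit days.

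The measure is also uncertain. *Aggregate drug compliance* is not defined: it could be the tablet count of SAP Section 9.3.23.5 or the aggregate diary measure of Section 9.3.23.7, which averages study drug, food and glucocorticoid diary compliance. Section 12.1 favours the tablet count; the word *aggregate* appears in the diary definition.

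The consequence is modest. It reaches the PP repeat of the primary analysis and any optional PP analysis of the secondary endpoints. The ITT primary result does not change. The 78.4% and 84.9% figures are correct arithmetic on assumed splits, and nothing in the documents shows how many subjects would be affected or how far a PP estimate would move. The change is still worth making, because a supportive analysis needs a population fixed by rule.

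**What to change.** Replace the bullet in SAP Section 8.3 with: *study drug compliance below 80% over Part A (first double-blind dose to the end of Part A dosing), calculated per Section 9.3.23.5*.

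Add three clarifications:
- How early discontinuation enters the denominator: planned Part A days or days on drug.
- Which date ends Part A dosing. Protocol Section 6.1.2 keeps subjects on their assigned drug after the Week 18 visit until new supply arrives, and SAP Section 9.3.23.3 ends a period the day before the next one starts. The date chosen must be known at the lock.
- That the existing requirement to identify the PP set before database lock means the Week 18 hard lock.

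Record the new window in SAP Section 15. The cost is a few lines of text. No new data are needed, and Part A compliance is already planned output under SAP Section 12.1.

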### **8.4 Safety Analysis Set**

The Safety (SAF) Analysis Set is defined as all subjects who received at least one dose of study drug (tildacerfont or placebo) during the Treatment Period, summarized by actual drug received.

### **8.5 Randomized Safety Analysis Set**

The Randomized Safety (RSAF) Analysis Set is defined as all subjects who received at least one dose of randomized study drug (tildacerfont or placebo) during the Treatment Period. The randomized safety analysis set, which will be based on the actual treatment received, will be used for evaluation of general medical history, study drug exposure, concomitant medication, and safety.

### **8.6 Pharmacokinetic Analysis Set**

The Pharmacokinetic (PK) analysis set will include all randomized subjects who receive at least one dose of tildacerfont and have at least one evaluable PK sample.

## **9 GENERAL CONSIDERATIONS**

Data summarization and presentation conventions are documented in a separate document for mock-shells.

For all summaries of Part A by treatment, the columns will minimally include the randomized treatment groups of placebo, 50 mg tildacerfont, 100 mg tildacerfont, and 200 mg tildacerfont. All other summaries will use actual dose level unless otherwise specified.

### **9.1 Presentation of Summary Statistics**

For most summary statistics, data will be analyzed and displayed in tabular format.

Unless otherwise specified, continuous serum hormones (A4, 17-OHP, ACTH) will be summarized using a 11-point descriptive statistics (i.e., n, mean, standard deviation [SD], median, 25% quartile [Q1], 75% quartile [Q3], minimum, maximum, geometric mean, geometric coefficient of variance [CV%], 95% confidence interval [CI] for geometric mean [including geometric mean ratio and its 95% CI]).

All other continuous variables will be summarized using an 8-point descriptive summary (n, mean, SD, median, Q1, Q3, minimum, and maximum) unless otherwise specified.

The same number of decimal places as in the observed value will be presented when reporting minimum and maximum; 1 additional decimal place than in the observed value will be presented when reporting mean, median, Q1, Q3, geometric mean, 95% CI; 2 additional decimal places than in the observed value will be presented when reporting SD. Geometric CV% will be reported to one decimal place. All percentages will be presented to 1 decimal place, unless otherwise specified.

All categorical/qualitative data will be presented using the frequency of events and percentages. Percentages equal to 100 will be presented as 100% and percentages will not be presented for zero frequencies. For summaries of AEs and concomitant medications (CMs), the percentages will be based on the number of subjects who received the study drug dose within the period that is being summarized.

All analyses and summaries will be produced using SAS® version 9.4 or higher.

## **9.2 Presentation of p-values**

Results of statistical analyses will be reported using summary tables, listings, and figures (TLFs). The ICH of Technical Requirements for Pharmaceuticals for Human Use numbering convention will be used for all CSR TLFs.

Unless otherwise noted, all statistical testing will be two-sided and will be performed at the 0.05 significance level. Tests will be declared statistically significant if the calculated p-value is < 0.05, unless otherwise specified. P-values will be reported with 4 significant digits except when reporting p-values less than 0.001, reported as < 0.001.

## **9.3 Definitions and Derived Variables**

### **9.3.1 Screened and Enrolled Subjects**

#### **9.3.1.1 Screened Subjects**

Subjects who signed an informed consent form are considered Screened Subjects

